1.2.6.2 Secondary endpoints

To analyze the changes from baseline on Weeks 3 and 21 for intraepidermal nerve fiber density and branching by PGP9.5 antibody staining in lesional skin, the summary plots for AD participants based on the mITT population (and on the ITT population, if applicable) will be graphs of mean +/- SEM for raw data, absolute and percent change from baseline at baseline (ie, 0), Week 3 and Week 21.

To analyze the changes from baseline on Weeks 3 and 21 for intraepidermal nerve fiber density and branching by PGP9.5 antibody staining in lesional skin and changes from baseline over time and at Weeks 17 and 21 for the outcomes of the assessments/questionnaires (peak pruritus assessed by numeric rating scale (NRS), eczema and severity index (EASI), scoring atopic dermatitis (SCORAD), patient-reported outcomes measurement information (PROMIS-itch), patient oriented eczema measure (POEM), dermatology life quality index (DLQI), atopic dermatitis control tool (ADCT) and sleep quality/skin pain/skin sensitivity/skin burning NRS), the individual profiles over time will be spaghetti plots on raw data with all the AD participants on the same graph and the AD group mean.

To analyze the changes from baseline over time and at Weeks 17 and 21 for the outcomes of the assessments/questionnaires, the following variables will be analyzed:

- Peak pruritus assessed by numeric rating scale (NRS): scale of the worst itch (from 0 ("no itch") to 10 ("Worst itch imaginable")).
- Eczema and severity index (EASI): composite index ranging from 0 to 72 calculated as follows. The intermediate and total EASI scores will be derived, however, only the total EASI score will be analyzed.
 - Severity scores: for each region (Head and neck, Trunk, Upper limbs and Lower limbs), the severity score will be derived as follows, ranging from 0 to 12:

$$\text{Severity score}_R = \text{Intensity score}_{\text{Erythema}, R} + \text{Intensity score}_{\text{Edema/Papulation}, R} + \text{Intensity score}_{\text{Excoriation}, R} + \text{Intensity score}_{\text{Lichenification}, R},$$

where R = region.

- Region scores: for each region, the region score will be derived as follows:

$$\text{Region score}_R = \text{Severity score}_R * \text{Area score}_R * \text{Multiplier}$$

where R = region, Multiplier = 0.1 for Head and Neck region, 0.3 for Trunk, 0.2 for Upper Limbs, 0.4 for Lower Limbs.

- Total EASI score will be derived as the sum of the 4 region scores.
- Scoring Atopic Dermatitis (SCORAD): intermediate SCORAD scores (A/B/C) and total SCORAD score calculated as follows. The intermediate and total SCORAD scores will be derived, however, only the total SCORAD score will be analyzed.

$$\text{SCORAD score} = A/5 + 7*B/2 + C, \text{ where}$$

A is the sum of each extent of AD (Left and Right Lower Limbs, Left and Right Upper Limbs, Anterior Trunk, Head and Neck, Genitalia and Posterior Trunk) in %;

B is the sum of severity scales of each symptom of AD (Dryness, Edema/Papulation, Erythema, Excoriation, Lichenification and Oozing/Crust) (scale from 0 to 3);

C is the sum of visual analogue scale (VAS) of itch and sleeplessness (VAS from 0 to 10).

- Investigator global assessment (IGA): 5-point scale to rate the severity of AD globally ranging from 0 (clear) to 4 (severe).
- Patient-Reported Outcomes Measurement Information (PROMIS-itch):
 - Itch-Severity: scores of each of 7 quantitative items and total score.
 - Itch-Activity and Clothing: scores of each item.
 - Itch-Mood and Sleep: scores of each item.
 - Itch-Interference: scores of each item.
 - Itch-Scratching Behavior: scores of each item.
 - Itch-Quality and Itch-Triggers: not applicable (Yes-No answers).
- Patient Oriented Eczema Measure (POEM): total score (sum of the 7 items) ranging from 0 to 28. A high score indicates a high severity.
- Dermatology Life Quality Index (DLQI): total score (sum of the 10 items) ranging from 0 to 30. A high score indicates a poor quality of life (QoL).
- Atopic Dermatitis Control Tool (ADCT): total score (sum of the 6 items) ranging from 0 to 24. A high score indicates a low AD control.
- Sleep Quality NRS: scale of the sleep quality [from 0 (“Worst possible sleep”) to 10 (“Worst pain possible”)].
- Skin Pain NRS: scale of the skin pain [from 0 (“No pain”) to 10 (“Worst pain possible”)].
- Skin Sensitivity NRS: scale of the skin sensitivity [from 0 (“Normal”) to 10 (“Extremely sensitive”)].
- Skin Burning NRS: scale of the skin burning [from 0 (“Not at all”) to 10 (“Very much”)].

To analyse the proportion of AD participants reaching pruritus NRS ≥ 4 point improvement from baseline at Weeks 3, 7, 11, 15, 17 and 21 for each NRS scale (Sleep Quality, Skin Pain, Skin Sensitivity and Skin Burning), a participant will be considered to reach a pruritus NRS ≥ 4 point improvement at a given time point if he presents a change from baseline ≥ 4 at the timepoint.

1.2.6.3 *Exploratory endpoints*

Not applicable (biomarker analyses).

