5.1.1 Atopic dermatitis patients

Age

I 01. Male or female of ≥ 18 years of age inclusive, at the time of signing the informed consent form (ICF).

Type of participant and disease characteristics

I 02. Diagnosed with moderate-to-severe chronic AD for at least 1 year before screening.

I 03. Eligible to be treated with dupilumab according to product monograph.

I 04. Pruritus lasting 6 or more weeks before baseline (Day 1).

I 05. Eczema Area and Severity Index (EASI) score ≥ 12 at baseline.

I 06. Pruritus numerical rating scale (NRS) ≥ 4 at baseline.

I 07. Investigator global assessment (IGA) score of ≥ 3 at screening (on the 0 to 4 scale) at baseline.

I 08. Atopic dermatitis active lesions on the upper limbs or lower limbs suitable for a skin biopsy without oozing, bleeding, or infection on upper limbs or trunk.

I 09. Patients with acute AD lesions as determined by Investigator's judgment.

I 10. Participants able to accept skin biopsy procedure.

- I 11. Participants willing to refrain from applying any emollients or topical medications on the target assessment areas (including lesional and non-lesional) throughout the study unless necessary to treat intolerable symptoms.
- I 12. Participants willing and able to comply with all site visit and study-related procedures.
- I 13. Participants able to understand and complete all patient related outcome assessments and questionnaires.

Concomitant medication

- I 14. Stable treatment with non-prohibited medication ([Section 6.5.2](#)) or therapy during the study.

Informed consent

- I 15. Capable of giving signed informed consent which includes compliance with the requirements and restrictions listed in the ICF and in this protocol. In countries where legal age of majority is above 18 years, a specific ICF must also be signed by the participant's legally authorized representative.

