8.1.1.6 Skin pain numerical rating scale

Skin pain NRS is a one-item PRO measure asking the patients to rate their skin pain using a 0 (“No pain”) to 10 (“Worst pain possible”) NRS. Patients will be asked the following question:

“Think about all the areas of your skin with eczema. How would you rate your skin pain at its worst in the past 24 hours?”

The skin pain NRS will be assessed at time points according to [Section 1.3](#).

The skin pain NRS is provided in the study reference manual.

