8.1.1.7 Skin sensitivity to touch numerical rating scale

Skin sensitivity to touch NRS is a 1 item PRO measure asking the patients to rate their skin sensitivity to touch using a 0 (“Normal”) to 10 (“Extremely sensitive”) NRS.

Participant will be asked the following question: "Think about all the areas of your skin with eczema. How sensitive was your skin at its worst in the past 24 hours?"

The skin sensitivity to touch NRS will be assessed at time points according to [Section 1.3](#).

The skin sensitivity to touch NRS is provided in the study reference manual.

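### The SAP's 4-point responder rates for sleep quality, skin pain, sensitivity and burning have no baseline condition, so participants who cannot gain 4 points cap each rate

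*SAP*

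**What the plan says.** The protocol has one NRS responder endpoint, a 4-point improvement in pruritus, summarised on the mITT population (Table 4, section 9.4.7). SAP 1.2.6.2 carries the same threshold to other scales. The sentence opens "To analyse the proportion of AD participants reaching pruritus NRS ≥ 4 point improvement from baseline" and continues, after a list of weeks, "for each NRS scale (Sleep Quality, Skin Pain, Skin Sensitivity and Skin Burning"). A participant counts as a responder "if he presents a change from baseline ≥ 4 at the timepoint". That is the whole rule: it has no baseline condition, no stated denominator and no sign.

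The weeks listed (3, 7, 11, 15, 17 and 21) are the post-baseline weeks at which the protocol schedule (section 1.3) collects these four scales. They are not the protocol's pruritus responder weeks (3, 5, 9, 17 and 21). The four analyses therefore look intended, although the sentence still calls the outcome pruritus.

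Among the AD inclusion criteria, only one NRS has a minimum: "Pruritus numerical rating scale (NRS) ≥ 4 at baseline". The other severity minima are "Eczema Area and Severity Index (EASI) score ≥ 12 at baseline" and an IGA of at least 3. Neither fixes a floor for pain, sensitivity, burning or sleep.

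**The concern.** A 4-point responder rule is attainable for pruritus because I 06 admits nobody below 4. The SAP moves the rule to four scales without that protection. A participant may qualify on itch, EASI and IGA and still report little skin pain or burning, or sleep well, at baseline. That participant has no room for a 4-point improvement and can only be counted as a non-responder.

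Each rate then mixes two things: how many participants had the symptom badly enough at baseline, and how many of those improved. A low rate for skin pain could mean little effect on pain or little pain to begin with, and the percentage alone does not say which. This matters because the protocol wants the study to generate hypotheses and to guide the design of a larger one (sections 1.1 and 2.2).

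**Working it through.** The documents give no expected responder rate and no baseline distribution for these scales, so there is no planned figure to reproduce. The check is arithmetic on the scales.

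**Inputs**
- Skin pain, sensitivity to touch and burning: 0 to 10, lower is better (protocol 8.1.1.6 to 8.1.1.8).
- Sleep quality: 0 to 10, higher is better (protocol 8.1.1.9). The SAP's description of this scale repeats the pain scale's upper anchor, so the direction is taken from the protocol.
- Threshold: 4 points (SAP 1.2.6.2).
- AD participants: 34 (protocol section 5). Planned drop-out: 20% (protocol 9.2), so 34 × 0.80 = 27.2, about 27.
- No imputation (SAP 1.2.6).
- Assumed, because the documents are silent: the share *f* whose baseline rules out response, and the rate *r* among those able to respond.

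**Step 1. Baselines that rule out response**
- A fall of 4 needs baseline − 4 ≥ 0. Baselines 0, 1, 2 and 3 fail (pain, sensitivity, burning).
- A rise of 4 needs baseline + 4 ≤ 10. Baselines 7, 8, 9 and 10 fail (sleep quality).

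**Step 2. Ceiling on the reported rate**

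Ceiling = (N − number affected) / N = 1 − *f*.

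| N | Affected | Ceiling |
|---|---|---|
| 34 | 0 | 100% |
| 34 | 3 | 31/34 = 91.2% |
| 34 | 7 | 27/34 = 79.4% |
| 34 | 10 | 24/34 = 70.6% |
| 27 | 3 | 24/27 = 88.9% |
| 27 | 5 | 22/27 = 81.5% |
| 27 | 8 | 19/27 = 70.4% |

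**Step 3. Effect on a given rate**

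Reported rate = (1 − *f*) × *r*. With *r* assumed to be 60%, in whole participants out of 34:

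| Affected | Able to respond | Responders | All participants | Able participants only |
|---|---|---|---|---|
| 0 | 34 | 20 | 20/34 = 58.8% | 20/34 = 58.8% |
| 3 | 31 | 19 | 19/34 = 55.9% | 19/31 = 61.3% |
| 7 | 27 | 16 | 16/34 = 47.1% | 16/27 = 59.3% |
| 10 | 24 | 14 | 14/34 = 41.2% | 14/24 = 58.3% |

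The last column stays near 60% apart from rounding to whole people, while the all-participant rate falls with the number affected. With 10 affected and *r* = 40%, the pair is 10/34 = 29.4% and 10/24 = 41.7%. With *r* = 80%, it is 19/34 = 55.9% and 19/24 = 79.2%.

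**The case against.** **The denominator is a reading.** SAP 1.2.6.2 says when a participant reaches the improvement. It names no denominator for these scales, and the mITT basis in the protocol belongs to the pruritus endpoint. A reader might infer that the SAP expressly classes low-baseline participants as failures; it does not. All AD participants with data is still the natural reading of a proportion of AD participants. The SAP does limit percentages to evaluable participants for nerve fiber branching (1.2.6.1), but says nothing similar here. The objection stands as a qualification.

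**The rule has no sign.** Read literally as post-baseline minus baseline, a change of 4 or more is a worsening on pain, sensitivity and burning, and a participant going from 3 to 7 on pain would meet it. The ceiling on those three scales therefore rests on the stated intent, improvement. This stands, and the sign needs correcting in the same edit.

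**Little depends on these rates.** A reader might infer that a planned comparison across the four scales, or with pruritus, is spoiled. Neither document plans one. The study is single-arm with no formal testing, and summaries of raw values and changes, individual plots and listings will show the baselines. This limits the consequence, though a published percentage is often read without its listing.

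**The size is unknown.** A reader might infer that a third or a half of participants are affected. Nothing in the documents supports that, and the share could be close to zero on some scales.

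**Restricting the denominator has its own faults.** The eligible subsets differ by scale. A participant at exactly 4 must reach 0 to respond, so baseline mix still matters, as it does for pruritus. In an uncontrolled study, selecting on a worse baseline score adds some regression to the mean, which tends to raise the restricted rate. All of this stands, and it is why both rates should be shown.

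**Conclusion.** The point holds as a matter of reporting and interpretation. Without a baseline condition, each of the four rates is capped at one minus the share of participants who start below 4 on pain, sensitivity or burning, or above 6 on sleep quality. This rests on two assumptions: the denominator is all AD participants with data, and the rule is meant to capture improvement. The cap is arithmetic; its size in this trial cannot be known from the documents. The illustrative ceilings of 91%, 79% and 71% assume 3, 7 or 10 affected out of 34, and the counts will be smaller after the planned 20% drop-out.

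The documents do not support a claim that the all-participant rate is illegitimate, or that a test, an error rate or the primary endpoint is affected. The correction is worth making because it is cheap and uses data already collected.

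**What to change.** In SAP 1.2.6.2, add for each scale:
- The responder rate among participants whose baseline allows a 4-point improvement: baseline at least 4 for skin pain, sensitivity and burning, at most 6 for sleep quality. Show that n beside the percentage.
- The all-participant rate next to it, with its denominator stated.
- The direction of improvement: a decrease of at least 4 for pain, sensitivity and burning, an increase of at least 4 for sleep quality. Name the scale instead of pruritus.

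The cost is a short edit to one SAP paragraph and an extra line per table; no new data are needed. The downsides are a smaller n per scale, some regression to the mean from selecting on baseline, and denominators that differ between scales. A table footnote should say that the restricted rates are not a head-to-head comparison of the scales.

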| β-HCG test (if applicable) ^l | X | X ^a | | | | X | | | | | X | X | |
| FSH | X | | | | | | | | | | | | |
| Adverse event collection | | | | | | | | | | | | | |
| Photography (lesional skin) | | X | | | | X | | | | | X | X | |
| Clinician Reported Outcomes (ClinRO) | | | | | | | | | | | | | |
| IGA | X | X | | | | | | | | | X | X | |
| EASI | | X | | X | | X | | | | | X | X | |
| SCORAD | | X | | X | | X | | | | | X | X | |
| Patient-Reported Outcomes (PRO) | | | | | | | | | | | | | |
| Peak pruritus NRS ^{m, n} | | X | X | X | X | X | X | X | X | X | X | X | |
| Sleep quality NRS + Skin pain + Sensitivity NRS + Burning NRS ^m | | X | | X | | X | | X | | X | X | X | |

| Phase | Screening | Treatment period | | | | | | | | | | Follow-up | |
|-------------|-------------|------------------|----|-----|-----|-----|-----|-----|-----|-----|----------------|-----------|------|
| | | D1 | D8 | D15 | D29 | D43 | D57 | D71 | D85 | D99 | D113 | D141 | D197 |
| Day | D-28 to D-1 | W1 | W2 | W3 | W5 | W7 | W9 | W11 | W13 | W15 | W17 (EoT) | W21 (EoS) | W29 |
| Week | W-4 to W0 | | | | | | | | | | | | |
| Visit | 1 | 2 ^a | | 3 | | 4 | | | | | 5 ^b | 6 | |
| POEM | | X | | | | X | | X | | X | X | X | |
| PROMIS-itch | | X | | | | X | | X | | X | X | X | |
| DLQI | | X | | | | X | | X | | X | X | X | |
| ADCT | | X | | | | | | | | | X | X | |

Abbreviations: ADCT: Atopic Dermatitis Control Tool; ClinRO: Clinician Reported Outcomes; d: day; DLQI: Dermatology Life Quality Index; EASI: Eczema and severity index; eDiary: electronic diary; EoS: end of study; EoT: end of treatment; FSH: Follicle-stimulating hormone; IgE: immunoglobulin E; IGA: Investigator global assessment; IMP: investigational medicinal product; NRS: numeric rating scale; POEM: Patient Oriented Eczema Measure; PRO: patient-reported outcome; PROMIS: Patient-Reported Outcomes Measurement Information; SCORAD: Scoring Atopic Dermatitis; V: visit; w: week; β-HCG: β-Human chorionic gonadotropin.

- a All assessments at Baseline Visit (V2) are to be conducted prior to IMP administration.

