8.1.1.9 Sleep quality numerical rating scale

Sleep quality NRS is a one-item PRO measure asking patients to rate the quality of their sleep using a 0 (“Worst possible sleep”) to 10 (“Best possible sleep”) NRS. Patients will be asked to complete the following question upon awakening:

“Select the number that best describes the quality of your sleep last night.”

The Sleep Quality NRS will be assessed at time points according to [Section 1.3](#).

The sleep quality NRS is provided in the study reference manual.

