| Secondary | 
Changes from baseline on Weeks 3 and 21 for intraepidermal nerve fiber density by PGP9.5 antibody staining in lesional skinChanges from baseline on Weeks 3 and 21 for intraepidermal nerve fiber branching by PGP9.5 antibody staining in lesional skinRaw data and changes from baseline to Week 3 and Week 21; ie, absolute and percent changes, will be summarized with descriptive statistics (such as mean, median, SD, minimum, maximum, and 90% confidence interval) and plots for AD participants based on the mITT populationProfiles for baseline to Week 21 time points will be generated for individual values: eg, spaghetti plot and boxplot, and patients' group meansChanges from baseline over time and at weeks 17 and 21 for the outcomes of the following assessments/questionnaires
Peak pruritus assessed by numeric rating scale (NRS)Eczema and severity index (EASI)Scoring Atopic Dermatitis (SCORAD)Patient-Reported Outcomes Measurement Information (PROMIS-itch)Patient Oriented Eczema Measure (POEM)Dermatology Life Quality Index (DLQI)Atopic Dermatitis Control Tool (ADCT)Sleep quality NRSSkin Pain NRSSkin Sensitivity NRSSkin Burning NRSRaw data and change from baseline; ie, absolute and percent changes, will be summarized with descriptive statistics (such as mean, median, SD, minimum, maximum, and 90% confidence interval) for AD participants based on the mITT populationProfiles for baseline to Week 17, and baseline to Week 21 time points will be generated for individual values: eg, spaghetti plot and boxplot, and patients' group meansProportion of AD participants reaching pruritus NRS ≥ 4 point improvement from baseline at Weeks 3, 5, 9, 17 and 21
Number and percentage of AD participants reaching pruritus NRS ≥ 4 point improvement from baseline will be reported by time points based on the mITT populationBarplot over time of proportion of AD participants reaching pruritus NRS ≥ 4 point improvement from baseline will be produced. |

| Endpoint | Statistical analysis methods |
|---|---|
| Exploratory | |
| | |

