1 STATISTICAL AND ANALYTICAL PROCEDURES

1.1 INTRODUCTION

The purpose of this document is to provide additional technical details.

A comprehensive and detailed description of strategy and statistical technique used to perform the analysis of data was provided in Section 9 of the protocol (Version 1 dated on 17AUG2020 and Amended version dated on 06JAN2021).

As specified in the protocol, the biomarker analyses will not be part of this document and a specific dedicated statistical analysis plan (SAP) will be produced in addition to this statistical technical document (STD).

Adverse events and medical history terms will be coded according to the Medical Dictionary for Regulatory Activities (MedDRA Version 25.0).

Previous and concomitant medication records will be coded according to the World Health Organization Drug Dictionary (WHO-DD version March 2022).

The reporting of the safety statistical analyses will be programmed according to the recommendations and templates of the BTD-009094 “Summarizing and reporting standard Early Development clinical trial data (except oncology)” Version 4.0 dated 02-Feb-2021. For vital signs parameters, the analyses of abnormalities will be based on the definitions of potentially clinically significant abnormalities (PCSAs) from BTD-009536 “Analysis and reporting of safety data from Clinical Trials through the Clinical Study Report” Version 3.0 dated 24-May-2014 (Appendix 3) and displayed in [Section 3.1](#).

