3 APPENDICES

3.1 POTENTIALLY CLINICALLY SIGNIFICANT ABNORMALITIES CRITERIA

CRITERIA for POTENTIALLY CLINICALLY SIGNIFICANT ABNORMALITIES for Phase 2/3 studies (oncology excepted)		
Parameter	PCSA	Comments
Vital signs		
HR	≤50 bpm and decrease from baseline ≥20 bpm ≥120 bpm and increase from baseline ≥20 bpm	To be applied for all positions (including missing) except STANDING.
SBP	≤95 mmHg and decrease from baseline ≥20 mmHg ≥160 mmHg and increase from baseline ≥20 mmHg	To be applied for all positions (including missing) except STANDING.
DBP	≤45 mmHg and decrease from baseline ≥10 mmHg ≥110 mmHg and increase from baseline ≥10 mmHg	To be applied for all positions (including missing) except STANDING.

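### The Week 5 itch responder rate has no analysis visit in the SAP, and the SAP's only responder rule is misnamed and gives no direction

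*SAP*

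**What the plan says.** **Protocol.** Section 3 (Table 1) and Section 9.4.7 (Table 4) define one responder endpoint, on the pruritus NRS at Weeks 3, 5, 9, 17 and 21. Table 4 gives its analysis: "Number and percentage of AD participants reaching pruritus NRS ≥ 4 point improvement from baseline will be reported by time points", in the mITT population. The schedule in Section 1.3 marks peak pruritus at Day 29 (Week 5), and its footnote n sets daily assessment for 28 days, then weekly from Day 29. Section 8.1.1.9 scores sleep quality from worst at 0 "to 10 (“Best possible sleep”) NRS".

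**SAP, responder rule.** Section 1.2.6.2 has one responder rule. It carries the pruritus NRS name, but it is set for "Weeks 3, 7, 11, 15, 17 and 21 for each NRS scale (Sleep Quality, Skin Pain, Skin Sensitivity and Skin Burning"). A participant responds "if he presents a change from baseline ≥ 4 at the timepoint". The same section lists "Sleep Quality NRS: scale of the sleep quality [from 0 (“Worst possible sleep”) to 10 (“Worst pain possible"), so both sleep anchors read as worst.

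**SAP, windows.** Section 1.2.2 says that, as a rule, every protocol time point should be described. Its peak pruritus table gives one-day windows for D2 to D28 and then goes straight to D36, which spans 29 to 39 days. Home dosing in the same table does have a D29 row. If several post-treatment records share a window, the one closest to the scheduled visit is used.

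**The concern.** There are three separate problems.

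- **Name and scope.** The only responder derivation in the SAP bears the protocol endpoint's name but does not include peak pruritus. It sits under Section 1.2, which lists changes from the protocol's statistical section, so a programmer could take it as a replacement.
- **Direction.** The criterion has no sign, and the four scales do not all run the same way. The misprinted anchor falls on sleep quality, the scale that differs.
- **Week 5.** With no D29 window, the table of itch responders cannot contain a correctly identified Week 5 column.

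At stake are reported percentages for the trial's central symptom. A responder rate could be computed in the wrong direction or mistaken for the itch endpoint, and one prespecified time point could be lost or mislabelled.

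**Working it through.** The plan states no figure to reproduce here, so the check sets its rules against each other.

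**1. Weeks to days.** The schedule follows study day = 7 × (week − 1) + 1, with first dose on Day 1.

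- Protocol responder weeks 3, 5, 9, 17, 21 are Days 15, 29, 57, 113, 141.
- SAP rule weeks 3, 7, 11, 15, 17, 21 are Days 15, 43, 71, 99, 113, 141. These are exactly the post-baseline collection days of the four other scales in protocol Section 1.3.

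The two lists share Weeks 3, 17 and 21. The SAP list lacks 5 and 9 and has 7, 11 and 15.

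**2. Assigning the itch records to windows.** The table counts days after first dose without saying whether the dosing day is Day 1 or day 0. SAP Section 1.3 sets first dose = Day 1, but for listings. Both readings were tried:

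| Protocol week | Study day | Visit if windows are study days | Elapsed days | Visit if windows are elapsed days |
|---|---|---|---|---|
| 3 | 15 | D15 | 14 | D14 |
| 5 | 29 | D36 (29 to 39) | 28 | D28 |
| 9 | 57 | D57 (54 to 60) | 56 | D57 |
| 17 | 113 | D113 (110 to 116) | 112 | D113 |
| 21 | 141 | D141 (138 to 197) | 140 | D141 |

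- **Study-day reading.** Day 29 is 36 − 29 = 7 days from the D36 target. Days 30 to 39 are at most 6 days away. The closest-record rule therefore keeps Day 29 only when the window holds no other record, and the scheduled Day 36 record normally displaces it.
- **Elapsed-day reading.** The Day 29 record is kept but labelled D28, and the Week 3 record is labelled D14, so 2 of 5 labels are one day early. A record one day after first dose has no window.

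Neither reading yields a Week 5 visit.

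**3. Counting weekly visits.** Protocol, D29 to D141: (141 − 29)/7 + 1 = 17. SAP, D36 to D141: (141 − 36)/7 + 1 = 16. The missing visit is D29.

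**4. Which reading fits the table.** All 14 rows from D43 to D134 are −3/+3 days around target in study days and −2/+4 in elapsed days, so study days fit better. In study days D36 alone is −7/+3 and 11 days wide, against 7 for those rows. That is the pattern left by an omitted D29 row.

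**5. Direction.** Change = post minus baseline.

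| Scale | Scores | Change | Meets change ≥ 4 | True 4-point improvement |
|---|---|---|---|---|
| Pain, sensitivity, burning | 8 to 3 | −5 | No | Yes |
| Pain, sensitivity, burning | 3 to 8 | +5 | Yes | No |
| Sleep quality (protocol anchors) | 3 to 8 | +5 | Yes | Yes |
| Sleep quality (protocol anchors) | 8 to 3 | −5 | No | No |

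Post minus baseline throughout reverses 3 of 4 scales. Baseline minus post throughout reverses 1 of 4. A direction chosen per scale reverses 0 of 4. Elsewhere the SAP does write the sign into a rule, as in "≤50 bpm and decrease from baseline ≥20 bpm" in Section 3.1.

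**The case against.** The strongest reply is that the intent is clear. The rule speaks of improvement, including in the clause that defines a responder, and the anchors for pain, sensitivity and burning stand just above it. Counting a rise in pain as improvement would contradict the sentence, so the reversals would be programming errors. This largely stands: the reversal counts show what a single sign would do, not what is expected. The criterion itself still lacks the direction, and the SAP's sleep anchors cannot supply it. The vital-sign comparison is only supporting evidence, because those criteria flag abnormality both ways and have to be signed.

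Second, the protocol endpoint is not withdrawn. The SAP says "The purpose of this document is to provide additional technical details" and refers to protocol Section 9 for the full description, which gives the scale, threshold, weeks and population. That also stands, and Week 9 does have a window (D57). The different weeks are no error in themselves, since they are the four scales' own schedule; the fault there is the wrong name. What the SAP does not supply is a derivation for the endpoint and a Week 5 visit.

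Third, the elapsed-day reading is the weaker one, as step 4 shows, and the practical loss is small: the Day 29 value stays in the listings and a D28 window lies one day earlier. This limits the consequence, but neither point puts Week 5 in the summary table.

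**Conclusion.** The concern holds and should be fixed. Followed as written, the window table leaves 1 of the 5 prespecified itch responder time points (Week 5) without an analysis visit under either day convention. On the better-fitting study-day reading, the Day 29 record is displaced by any record on Days 30 to 39. The SAP's one responder rule is misnamed, and its criterion cannot be applied with one sign to all four scales; the number reversed is 3, 1 or 0 of 4 depending on how it is programmed. The sleep anchor at 10 is wrong against the protocol.

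The reach is limited to secondary descriptive outputs. The primary nerve-fibre results are untouched, and because the protocol plans no formal testing, no error rate is affected. The conclusion assumes that itch records are collected as scheduled and that the closest-record rule is applied as stated.

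**What to change.** 1. **Day convention.** State that the windows are in study days, with first IMP dose = Day 1.
2. **Week 5 window.** Add peak pruritus D29 = study days 29 to 32 and start D36 at 33 (33 to 39, the same ±3 days as D43 to D134). Each day from 2 to 197 then falls in exactly one window. The exact D29 width is a choice that the documents do not dictate. If elapsed days are meant instead, lower every post-baseline peak pruritus bound by 1: D2 to D28 = 1 to 27, D29 = 28 to 31, D36 = 32 to 38, D43 = 39 to 45, and so on to D141 = 137 to 196.
3. **Itch responder.** Define it explicitly as peak pruritus NRS post minus baseline ≤ −4 at Weeks 3, 5, 9, 17 and 21.
4. **Other four scales.** If they are kept, list them as additional analyses under their own names: ≤ −4 for skin pain, sensitivity and burning, and ≥ +4 for sleep quality.
5. **Sleep anchor.** Correct the label at 10 to agree with protocol Section 8.1.1.9.

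The cost is SAP wording and a few programming lines. No new data are needed.
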